*** * * Background, Purpose, Study Procedures * * ***

Title

EpxCogScreen

Complete Sections 1 - 12. In sections that allow reference to a grant, clearly state section and page numbers. Any information that is different or specific to the local site should be in the SLU application. Specify N/A as appropriate.

1. Background/Rationale

Page numbers from a grant may be referenced in 1a.

- a) **Provide an introduction and background information, including a review of the literature. Describe any past findings leading to the formulation of the study. *?HELP?***

Telemedicine is a modern field of clinical medicine that incorporates telecommunication and information technology to diagnose and managing health care remotely. Interventions range from telephone reminders to remote physician consultation by videoconference. Simple technology such as telephones and SMS texting are ubiquitous forms of communication that have the potential to increase the frequency of physician-patient contact. Such improvements in communication may improve patient adherence, promote education and engagement, allow real-time collection of critical biometric and clinical data over time, and bridge the gap between recognizing adverse events and actual disease management.

One disease that could benefit from earlier detection is dementia. Dementia is characterized by a loss of cognitive functions, such as memory, comprehension, visual-spatial orientation, and judgment. The most common form of dementia is Alzheimer's disease, but vascular dementia and Lewy-body dementia can also cause cognitive impairment. It is estimated that 47.5 million people are affected with dementia worldwide and it is the most common form of disability in the geriatric population over the age of 65, affecting 1 in 9 people in that population [1]. A formal diagnosis for Alzheimer's relies primarily on clinical evaluation by a neurologist and neuropsychometric screens or tests to determine whether cognitive impairment exists.

In 2011, the Affordable Care Act added routine cognitive screening as a component of the Medicare Annual Wellness Visit, but did not recommend a universal screening tool [2]. This initiative was supported by many public organizations, including the Alzheimer's Association. Typical neuropsychometric tests such as the Mini-Mental State Exam (MMSE) are administered in the physician's office and can take 7 to 15 minutes to complete [3]. This addition to the wellness visits demonstrates the increasing value of early diagnosis for Alzheimer's and other dementias. However, time constraints during patient visits may cause the physician to forgo a thorough cognitive screen. Unlike the MMSE, the Rapid Cognitive Screen (RCS) is a 3 item screening tool that takes less than 5 minutes to complete. This screen has exhibited

Protocol Title: EpxCogScreen

screening tool that takes less than 5 minutes to complete. This screen has exhibited remarkable sensitivity and specificity in detecting both mild cognitive impairment (sensitivity=0.87, specificity=0.70) and dementia (sensitivity=0.89, specificity=0.94) in patients over the age of 65 [4]. In addition, higher scores (less impaired) on the screen are indicative of lower rates of mortality. Due to the simplicity of this screening tool, it can be transformed into an at-home, telemedicine screen that would eliminate the time constraints that serve as a barrier to early detection.

While the U.S. Preventative Services Task Force (USPSTF) does not currently recommend frequent cognitive screening, there is very little evidence of potential risks from early screening and diagnoses [5]. Cognitive screens are meant to increase awareness of a patient's neurocognitive changes, not to diagnose. A formal diagnosis can only be completed after a physical exam of the patient, including neurological and psychiatric evaluations and lab tests by a geriatrician or neurologist, which decreases the likelihood of false positives.

While there are no current disease-modifying therapies for dementia, the importance of early detection cannot be emphasized enough. An estimated 29-76% of Alzheimer's patients are undiagnosed because screening has not yet reached standard-of-practice in geriatric and primary care clinics [11-13]. The astounding number of undiagnosed patients would decrease with routine screening and would allow for patients and their caregivers to plan for their future. In addition, early intervention has been shown to delay placement into nursing homes, empower patients to be more involved with their care plan, and allow physicians to identify and manage comorbidities such as depression, malnutrition, and falls more effectively [6,7]. Delayed admission into nursing homes and fewer hospitalizations are associated with decreased healthcare costs for patients, their families, and the healthcare system [7, 14]. Furthermore, early detection will be critical for future pharmaceutical intervention, as nearly every major clinical trial for Alzheimer's is now targeting patients in the pre-clinical stage of disease [8-10].

- 1). Van der Linde RM, Dening T, Blossom CM, et al. "Longitudinal course of behavioural and psychological symptoms of dementia: systematic review" *The British Journal of Psychiatry*. 2016 Aug; DOI: 10.1192/bjp.bp.114.148403
- 2). Cordell, CB. et al. "Alzheimer's Association recommendations for operationalizing the detection of cognitive impairment during the Medicare Annual Wellness Visit in a primary setting" *Alzheimer's & Dementia: The Journal of the Alzheimer's Association*. 2012; 9: 141-150.
- 3). Ebell MH. "Brief screening instruments for dementia in primary care" *American Family Physician*. 2009 Mar; 15:79(6):497-500.
- 4). Malmstrom T, et al. "Rapid Cognitive Screen: Sensitivity and specificity for cognitive dysfunction and predictive validity for poor health outcomes" *Alzheimer's & Dementia: The Journal of the Alzheimer's Association*, Volume 9, Issue 4, P773
- 5). Final Recommendation Statement: Cognitive Impairment in Older Adults: Screening. U.S. Preventive Services Task Force. May 2015.
<https://www.uspreventiveservicestaskforce.org/Page/Document/RecommendationStatementFinal/cognitive-impairment-in-older-adults-screening>

Overall Hypothesis: The Epharmix caregiver administered Rapid Cognitive Screen will have statistically significant correlation to the screen administered by a healthcare professional in the clinic.

Aim: Patient- Provider Communication -- To determine if the Epharmix EpxCogScreen can be used to obtain more timely clinical data about cognitive impairment for ongoing physician review, than by traditional methods.

Please save frequently

- c) **Describe the study design (e.g., outline the experimental procedures, describe the ethnographic observation and/or interviewing procedures, or outline survey research methods). Also, indicate if the subjects will be randomized in this study.**

Patients and their caregivers at Saint Louis University Geriatric Clinic will be included in this study and both must consent to participate in the study. The designated caregiver will enroll in the Epharmix program and will receive SMS text messages after one month. The messages will remind the caregiver of when to administer the Rapid Cognitive Screen and give them the option to receive all instructions via text or to use directions from a handout that the caregiver received while in clinic. All patient responses will be recorded through text and all patients will have been previously screened in the geriatric clinic by a health care professional. If the patient has an at-home RCS score decrease of three or more points, the patient's physician will be notified immediately through the Epharmix system and can then contact the patient for follow-up. Subjects will have the ability to opt out of the study electronically via text and phone at any point during the study. The scores of the screen from clinic and home administration will then

Protocol Title: EpxCogScreen

be analyzed to determine if a caregiver administered Rapid Cognitive Screen has high correlation to the screen administered in the clinic. A decrease in the baseline clinic score of three or more points will send an alert to the physician so that they can further evaluate the patient.

The clinic scores will be compared to the at-home RCS scores to determine the correlation coefficient between the two. In addition, at home scores will be compared to clinical diagnoses of dementia obtained from chart review. This will determine the validity of EpxCogScreen use in the geriatric population.

3. Study Procedures

- a) Does this study involve conduct of research at multiple sites and the SLU PI is the direct recipient of a federal grant for this research? If yes, please complete and attach the Supplemental Application for Coordinating Center Activities. N

Page numbers from a grant may be referenced in 3b and 3c.

- b) Describe all study procedures; from recruitment through end-of-study, that the human subject must undergo in the research project. Please note: The box below is for text only. If you would like to add tables, charts, etc., attach those files in the Attachment section (#12).

Patients will be screened with the Rapid Cognitive Screen (RCS) in clinic as a part of the normal standard of care. Patients and caregivers will receive information about the study and a handout with instructions in the physicians office and can consent if they are interested in participating. If they enroll in the study, the caregiver will receive text message instructions for the RCS one month later. The caregiver can choose to administer the screen with instructions only via text or by using the handout received in the office. He/she will read the instructions to the patient and record responses via text message. The screen will take no more than 15 minutes to complete.

After the data is compiled from the at-home screen, a medical record review will occur. This will look at previously diagnosed medical conditions, which have been indicated in the "Epharmix Data Collection Sheet" in Section 12, and will compare this data to scores received on the RCS screens.

- c) Describe how data analysis will be performed (statistical tests, methods for evaluating data) and indicate the smallest group/unit for which separate reporting will occur. For studies involving a questionnaire, if data and reliability information are available, please describe or provide references. For full board, unfunded studies describe sample size determination and power analysis. If none, please justify.

Data analysis will occur between the patient's at-home and in-clinic RCS scores. The scores will be plotted against one another to determine the correlation between them. The total score correlation, along with the correlation for each individual component of the screen (free recall, clock-drawing, and insight). In addition, the sensitivity and specificity of the at-home screen will be determined based upon clinical diagnoses of patients based on chart review.

- d) State if audio/video recording or photographing of subjects will occur. Describe how the recordings will be maintained during and upon completion of the project. Describe what will

Protocol Title: EpxCogScreen

become of the recordings after use (e.g., shown at scientific meetings, erased, etc.). Please note audio or video recordings of voice and pictures or video recordings of a face or a unique body marking would be considered identifiers. Please address this in your response.

Please save frequently

- e) State if deception (including incomplete disclosure of study purpose/procedures) will be used. If so, describe the nature of the deception and provide a rationale for its use. Also, describe debriefing procedures or justify a waiver of the requirement to debrief. NOTE: for studies using deception, an alteration of consent must be justified in the Informed Consent section of the protocol (#9) and the debriefing script/statement must be uploaded in the Attachments section (#12). See IRB Deception Guidelines.
- f) Saint Louis University Hospital. All research involving Saint Louis University Hospital, including the Emergency Department, inpatient or outpatient services (including outpatient surgery at ABI and the infusion center at DOB) and medical record access, requires approval from the Saint Louis University Hospital Research Review Committee prior to study initiation. This effort is coordinated through the SLU Clinical Trials Office via eRS. This process is designed to facilitate compliance with state and federal regulations as they pertain to research in hospitals and clinical research billing. Documents should be submitted as soon as possible, or at the latest, concurrently with IRB submission. Please contact the Research Compliance Office at [name] or [contact] or the SLU Clinical Trials Office at [name] or [contact] for more information.
- X Not Applicable
Yes, study requires Saint Louis University Hospital review
- g) SSMSL. All research involving SSMSL locations (including Cardinal Glennon), including inpatient or outpatient services and medical record access, requires approval from the SSM STL or SSM Cardinal Glennon Research Business Review (RBR) prior to study initiation. This process is designed to facilitate compliance with state and federal regulations as they pertain to research in hospitals and clinical research billing. While researchers can begin to complete the SSM RBR form at any time, the form should not be submitted until the IRB and the CTO have approved the study. Please contact the SSMSL Office at [name] or [contact] for more information.
- X Not Applicable
Yes, study requires RBR review
- h) **ClinicalTrials.gov Registration and GCP Training. Is this project subject to the NIH GCP Training and ClinicalTrials.gov Registration Requirements?** Y

Protocol Title: EpxCogScreen

As of January 1, 2017, a new NIH policy mandated biomedical and behavioral "Clinical Trials" to be registered on ClinicalTrials.gov. In addition, NIH policy requires personnel on NIH "Clinical Trials" to take GCP training every three years. Please review relevant definitions here. Contact the CTO at [contact] with questions about registering on ClinicalTrials.gov and refer to the training page of the IRB website for information on NIH GCP Training requirements.

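### The sole hypothesis, a significant home–clinic correlation, cannot detect a systematic shift, yet the alert acts on an absolute 3-point fall that no stated analysis evaluates

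*Protocol*

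**What the plan says.** Section 2b gives a single hypothesis: "The Epharmix caregiver administered Rapid Cognitive Screen will have statistically significant correlation to the screen administered by a healthcare professional in the clinic". It names no minimum coefficient and no agreement criterion.

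Section 2c says the scores will "be analyzed to determine if a caregiver administered Rapid Cognitive Screen has high correlation to the screen administered in the clinic", with no figure for what counts as high, and adds: "The clinic scores will be compared to the at-home RCS scores to determine the correlation coefficient between the two". It also says that "at home scores will be compared to clinical diagnoses of dementia obtained from chart review", and that this will settle the validity of the tool in the geriatric population. The lay summary in 2a likewise ties validity to the correlation.

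Section 3c lists the analyses. For home against clinic: "The scores will be plotted against one another to determine the correlation between them", with the same for each component. Separately, "the sensitivity and specificity of the at-home screen will be determined based upon clinical diagnoses of patients based on chart review". No score cut-off is given.

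The alert is defined on the difference itself: "A decrease in the baseline clinic score of three or more points will send an alert to the physician" (2c). Section 5d describes the same notification for a fall exceeding 3 points, which is a different rule.

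On timing, section 3b says "the caregiver will receive text message instructions for the RCS one month later". Section 4h requires only that the patient has had an earlier RCS in the clinic and sets no maximum gap. Section 4a plans 100 patients and 100 caregivers, hence 100 pairs.

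**The concern.** The hypothesis asks whether patients keep roughly the same rank order at home and in clinic. The tool depends on something else: whether a home score can be set against a clinic score on the same scale and the difference acted upon. A shift is plausible, because the person giving the test changes from a health professional to a caregiver working from texts or a handout.

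If caregivers score systematically low, the alert fires too often. If they prompt or score generously, real falls are hidden. Correlation barely responds to either, and raising the bar from significant to high correlation does not help. The study could report a valid home screen without saying how far home scores lie from clinic scores.

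**Working it through.** **No figure to reproduce.** The protocol states no alpha, power, expected correlation, scale or SD. From the documents come the number of pairs (100) and the alert step (3 points). Everything else below is assumed.

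**Step 1: what significance requires.** At an assumed two-sided 0.05 with n = 100, the smallest significant coefficient is r = t/√(t² + n − 2), with t = 1.984 on 98 df. This gives 1.984/√(3.94 + 98) = 0.197, or r² of about 0.04. With a normal approximation and equal SDs of 2.5, r = 0.2 implies an SD of differences of 2.5 × √(2 × 0.8) = 3.16. The chance of a fall of 3 or more is then Φ(−3/3.16) = 17%, with neither bias nor decline.

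**Step 2: a shift is invisible to r.** For a constant b, cov(X, Y + b) = cov(X, Y) and var(Y + b) = var(Y), so r is unchanged. On a bounded scale, floor and ceiling alter this slightly.

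**Step 3: size under an assumed model.** True score T ~ N(6, 2.5²). Clinic score = T + error; home score = T + bias + error. Error SD is 1.2, both scores are rounded and clipped to 0–10, and there is no true change.

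| Home bias | r | Mean difference | Fall of 3 or more |
|---|---|---|---|
| −2 | 0.787 | −1.85 | 34.7% |
| −1 | 0.795 | −0.92 | 17.0% |
| 0 | 0.796 | 0.00 | 6.3% |
| +1 | 0.790 | +0.88 | 1.7% |
| +2 | 0.775 | +1.70 | 0.34% |

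**Step 4: what a study of 100 pairs would conclude.** In 20,000 simulated studies at each bias, r exceeded 0.197 every time (lowest value 0.53). The 95% CI for the mean home-minus-clinic difference excluded 0 in 100% of studies at a bias of 1 or 2 points, in about 78–79% at 0.5 point, and in 5% with no bias.

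**Step 5: range.** Over mean 5–7, true SD 2–2.5 and error SD 1.0–1.5, a 2-point bias moves r by at most 0.04 and a 1-point bias by at most 0.01. Falls of 3 or more occur in 32–39% (bias −2), 12–23% (−1), 3–11% (none), 0.6–4.7% (+1) and 0.1–1.6% (+2).

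**Step 6: true change.** With no bias, a true-change SD of 1 point gives falls of 3 or more in 9%. Adding a mean decline of 1 point gives 20%, close to the 17% from a bias of −1.

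**Step 7: the two alert wordings.** In the base case with no bias, 6.3% fall by 3 or more and 1.7% by more than 3.

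**The case against.** The strongest reply is that validity does not rest on correlation alone. Sensitivity and specificity against chart diagnosis are planned, and they respond to a shift. In the same model, with an assumed fixed cut-off of 5 and disease defined as a true score of 5 or less, they are 0.90/0.82 with no bias. They become 1.00/0.45 at −2, 0.98/0.64 at −1, 0.74/0.94 at +1 and 0.51/0.99 at +2. So even a 1-point shift would move one of the two by 16 to 18 percentage points. This stands, but only with a pre-set cut-off, which the protocol does not give. It also tests the level of the home score, not the change from the clinic score that triggers the alert. The planned plot could show a shift by eye, but it is there to establish the correlation.

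Second, agreement statistics might sit in a separate analysis plan. They might, but that would not alter the hypothesis the protocol fixes or its statement of what determines validity.

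Third, the alert is a follow-up step and not an endpoint, and the call in section 5d can identify a false alarm. That does limit the harm from extra alerts. It does nothing for a missed fall, which prompts no call. Section 2a says results reach the physician automatically, but a score biased upwards would look reassuring.

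Fourth, the simulated figures depend on the inputs. With error SD 0.5–2.5, true SD 1.5–2.5 and mean 5–8, falls of 3 or more range over 0–23% with no bias and 2–32% at bias −1. Near the ceiling (mean 8, SD 1.5, error SD 0.5), a +2 bias lowers r from 0.86 to 0.77. Noise therefore matters too, and r carries some information about it. Even that 0.77 is far above 0.197.

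**Conclusion.** The concern holds and should be fixed. Meeting the stated hypothesis says almost nothing about a systematic home–clinic difference, and the quantity that drives the alert is not evaluated. That r ignores a constant shift is algebra and needs no assumption, apart from small floor and ceiling effects. The size is illustrative: in the assumed base case, r varies by about 0.02 while falls of 3 or more vary about a hundredfold (34.7% against 0.34%).

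The practical consequence is bounded by the follow-up call and, if a cut-off is fixed in advance, by the accuracy analysis. The conflicting alert wording in 2c and 5d is a separate, smaller defect, but it leaves the crossing proportion without a single definition.

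**What to change.** In sections 2b, 2c and 3c, make agreement the main home–clinic analysis:

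- mean home-minus-clinic difference with 95% CI;
- Bland–Altman 95% limits of agreement with CIs;
- proportion of patients crossing the alert step, with 95% CI.

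An absolute-agreement ICC for the total and kappa for the components are optional. Keep the correlation and plot as description. Base the validity conclusion on agreement together with sensitivity and specificity, not on the significance of r.

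Record the clinic-to-home interval for each pair, show the differences against it, and state that agreement figures mix true change with measurement difference. Reconcile the alert wording in 2c and 5d; which version applies is for the investigators.

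The 100 pairs suffice. For an assumed SD of differences of 1.35–2.1, the 95% CI half-width is about 0.3–0.4 points for the mean difference and 0.5–0.7 for each limit of agreement. Wilson 95% CIs for the crossing proportion would be 0–3.7% at 0/100, 2.8–12.5% at 6/100 and 26.4–44.7% at 35/100.

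The cost is wording, the clinic screen date from records already under review, and modest extra analysis, with no added patient contact. The downsides are a harder bar than p < 0.05, agreement figures that look somewhat worse because they include true change, and no way for them alone to separate real decline from a biased home screen.

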***** Subject Population(a-g) *****

4. Subject Population - In the space below, please detail the participants that you are requesting to recruit (include description of each group requested).

a) Number of evaluable subjects to be accrued.

200 (100 patients and 100 caregivers)

Exceeding the number listed here is a protocol violation. Prior IRB approval is required if additional participants are to be accrued. If applicable, this number should be consistent with your power analysis described in 3b.

b) What is the expected age range of subjects? (For example: ≥ 18 yrs to 90 yrs).

Patients must be over the age of 65 to participate. Caregivers can be greater than 18 years old to 90.
--

c) Requested Participant Description (e.g., gender, ethnicity, socio economic status, etc.). Include description of each group requested.

The population used will include all genders, socioeconomic, and ethnic backgrounds. Both patients with and without diagnoses of dementia will be included in the study.
--

d) If including vulnerable populations (minors, pregnant women and fetuses, <a href=<https://www.slu.edu/Documents/research/IRB/Neonates.docx> target=_blank>neonates, non-English speaking, economically or educationally disadvantaged, prisoners, adults temporarily or permanently unable to consent for themselves): 1) provide the rationale for the importance of including this population in the research, and 2) specify the measures being taken to minimize risks to potentially vulnerable subjects. Click on hyperlinks to access <a href=<https://www.slu.edu/division-of-research-administration-home/institutional-review-board->

Protocol Title: EpxCogScreen

(irb)/general-guidelines target=_blank>SLU Guidelines containing additional considerations and strategies for mitigating risks.

Any patient that visits the geriatric clinic at SLU and is over the age of 65 is eligible to participate in the study. Cognitive impairment and dementia are prevalent in this population, and early diagnosis is important to allow for patients to plan for their futures and have early intervention in the disease. Screening tools are used for early diagnosis, and this study would determine if an at home dementia screen could be used in the general geriatric population for earlier detection of disease.

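### The hypothesis in 2b is met by any significant home-clinic correlation (observed r of about 0.20 with 100 pairs), whereas 2c asks whether the correlation is high

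*Protocol*

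**What the plan says.** Section 2b contains one overall hypothesis: that the home screen given by the caregiver "will have statistically significant correlation to the screen administered by a healthcare professional in the clinic". Section 2c describes the same comparison and says that the scores will be analysed to "determine if a caregiver administered Rapid Cognitive Screen has high correlation to the screen administered in the clinic". Neither section attaches a value to the coefficient.

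Section 2c then names two comparisons, home scores against clinic scores and home scores against dementia diagnoses taken from the chart, and concludes: "This will determine the validity of EpxCogScreen use in the geriatric population".

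Section 3c, on data analysis, says of the home and clinic scores: "The scores will be plotted against one another to determine the correlation between them". It covers the total score and each component, and adds: "In addition, the sensitivity and specificity of the at-home screen will be determined based upon clinical diagnoses of patients based on chart review". It gives no target for either measure.

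Section 4a sets accrual at "200 (100 patients and 100 caregivers"). Only patients are scored, so there are at most 100 home-clinic pairs. The protocol states no alpha, no sidedness and no minimum correlation.

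**The concern.** The two sections set different standards for one comparison, and the weaker standard is in the hypothesis. A significant correlation ordinarily means rejection of rho = 0. Here the same instrument is given to the same patient in clinic and again about a month later at home (section 3b), in a sample that includes patients with and without dementia (section 4c). Zero correlation is not a serious rival explanation in that setting, so rejecting it says little about whether the home version works.

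At stake is what the study may claim. A modest coefficient would let the investigators report their only hypothesis as confirmed, although by the standard of 2c the result would be disappointing. A bar for *high* that is chosen after the coefficient is known would not be a test.

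**Working it through.** The protocol gives no derivation of its sample size, so there is no figure to reproduce. The check asks what 2b demands at the planned size.

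**Inputs**
- Pairs: n = 100 (section 4a). Fewer completed pairs are considered as an assumption.
- Alpha: not stated. Two-sided 5% is assumed; one-sided 5% and two-sided 1% are shown as a range.
- Coefficient: Pearson correlation is assumed, because the protocol says only correlation.

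**Smallest observed r that is significant**

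r = t / sqrt(n − 2 + t²), with t the critical value on n − 2 degrees of freedom. For n = 100, two-sided 5%, t = 1.984:

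r = 1.984 / sqrt(98 + 3.94) = 0.197, and r² = 0.039.

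| Assumption | Critical r | Shared variance |
|---|---|---|
| n = 100, two-sided 5% | 0.197 | 3.9% |
| n = 100, one-sided 5% | 0.165 | 2.7% |
| n = 100, two-sided 1% | 0.257 | 6.6% |
| n = 80, two-sided 5% | 0.220 | 4.8% |
| n = 50, two-sided 5% | 0.279 | 7.8% |

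By Fisher's z, with standard error 1/sqrt(97), an observed r of 0.20 has a 95% interval of about 0.004 to 0.38.

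**Chance of meeting 2b at a given true correlation**

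Probability ≈ Φ(atanh(rho) × sqrt(97) − 1.96); the opposite tail is negligible.

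| True rho | atanh(rho) × sqrt(97) | Chance of significance |
|---|---|---|
| 0.10 | 0.99 | 17% |
| 0.20 | 2.00 | 51% |
| 0.30 | 3.05 | 86% |
| 0.40 | 4.17 | 99% |

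A true correlation of 0.30 is 9% shared variance, and 0.40 is 16%.

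**What a floor on the lower confidence limit would demand (illustration, n = 100)**

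Required observed r = tanh(atanh(floor) + 1.96/sqrt(97)), and 1.96/sqrt(97) = 0.199.
- Floor 0.60: tanh(0.693 + 0.199) = 0.71. Chance of passing at true rho 0.80: Φ((1.099 − 0.693) × 9.849 − 1.96) = about 98%.
- Floor 0.70: tanh(0.867 + 0.199) = 0.79. Chance of passing: about 62% at true rho 0.80 and about 97% at 0.85.

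**The case against.** **2b may not be the decision rule.** It is one sentence in an application form, and 3c names no p-value and no pass/fail rule; it estimates coefficients, sensitivity and specificity. That is fair. A reader might go further and infer that the validity conclusion would carry no evidence at all. The text does not support this: 2c rests validity on the comparison with chart diagnoses as well as on the correlation. However, the diagnostic analysis has no target and is not part of the hypothesis, so it leaves 2b as weak as before.

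**The two wordings may be compatible.** With 100 pairs, any coefficient that deserves to be called high is also significant, so 2b could be a minimum and 2c the real judgement. This holds in one direction only. Many significant coefficients are not high, and 2b counts them as success.

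**A separate analysis plan may define *high*.** It may, and the missing number alone is no finding. The finding is that the protocol's hypothesis uses a different and weaker standard than its own design section. A threshold set elsewhere would still leave 2b at odds with it.

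**The test is not a formality for a poor screen.** A reader might infer that a nearly unrelated home screen is almost certain to pass. It is not: the chance is about 17% at a true correlation of 0.10 and about even at 0.20. Success becomes very likely only from about 0.30 to 0.40.

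**The data are unharmed.** The coefficient and its interval can be reported whatever 2b says. This limits the severity, but a bar chosen after the result is seen remains unconvincing.

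**Conclusion.** The point holds as a mismatch between 2b and 2c, with the success criterion set too low in 2b. Under two-sided 5% and 100 pairs, both of which are assumptions about the final analysis, an observed r of about 0.20 confirms the hypothesis. Across the other assumptions in the first table the threshold stays between 0.165 and 0.279, that is, under 8% shared variance, so the conclusion does not depend on the unstated alpha or on moderate loss of pairs. A true correlation of 0.30 would confirm the hypothesis about 86% of the time.

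This should be corrected before home scores are examined. It does not invalidate the design or the data, and it does not strip the wider validity assessment of content. Whether a correlation of any size shows agreement between home and clinic scores is a separate question that this point does not settle.

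**What to change.** Use one criterion in 2b and 2c and repeat it in 3c: the lower limit of the two-sided 95% confidence interval for the home-clinic coefficient of the total score exceeds a stated floor. The sponsor should choose and justify the floor and fix it before any home score is seen. The values 0.60 and 0.70 in the working are illustrations only; nothing in the protocol supports a particular number. Report the coefficient with its interval, and do not use a p-value against zero as the success rule.

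The cost is a sentence or so in each section, with no added patients, visits or data items. The price is a harder target: with a floor of 0.70, for example, a home screen whose true correlation is 0.80 would pass only about 62% of the time with 100 pairs, so the floor should be chosen with that in view.
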